#### 9.4.2. Safety Analyses

All DLT modeling will be performed on the DLT-evaluable population. All other safety analyses will be performed on the Safety Population. The statistical analysis methods to be used during the safety analyses by endpoint is presented in Table 17.

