Advancement to higher combination dose levels during the escalation phase will occur after an evaluation of safety and tolerability by the Dose Committee. The proposed continual reassessment method (CRM) will generate dose combination recommendations. The model estimates the probability of dose limiting toxicities (DLTs) in Cycle 1 (C1) at each candidate combination dose level to determine the dose combination to treat the next cohort. The MTD is selected as the combination associated with the highest posterior probability of DLT rating within the target interval of 25% - 35% and which have been used to treat at least 6 participants.

During escalation, a minimum of 3 participants on a combination dose level are required to be DLT evaluable to render a decision to proceed to the next dose level. A 4th participant, if available, may enroll onto the escalation dose before the first 3 participants have completed the DLT evaluation. DLT events for all participants at a given combination dose level will be entered into the CRM model and assessed by the Study Dose Committee. The first cycle (28 days) constitutes the DLT assessment period. Parallel Dose-Escalation Cohorts may be allowed.

***Dose-Expansion Component:*** After the Dose-Escalation Component has ended and the RP2D is determined, a Dose-Expansion cohort of up to 90 participants (including those already enrolled at this dose in the Dose-Escalation and Expansion cohorts) will be enrolled at the RP2D. In this Dose-Expansion cohort, up to 15 participants in each of the 6 genotypic/histotypic cohorts will be enrolled.

Moreover, once the Dose-Escalation Component has reached a threshold of activity based on clinically meaningful reduction in tumor burden at a dose with acceptable toxicity, additional participants may possibly be enrolled at dose levels prior to the determination of RP2D. The Dose Committee will determine whether clinically meaningful reduction has been achieved (eg,  $\geq 30\%$  reduction in the sum of longest diameters of target lesions or a lesser diminution with a preponderance of clinical evidence of benefit). See 'Dose-Escalation and Expansion Committee Charter' for more information.

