### 3. OBJECTIVES AND ENDPOINTS

#### 3.1. RMC-4630 and Cobimetinib Combination

Objectives	Endpoints

Primary
 

• To characterize the safety and tolerability of the combination of RMC-4630 and cobimetinib in participants with relapsed/refractory solid tumors

• To define the MTD and RP2D and schedules for the combination of RMC-4630 and cobimetinib in participants with relapsed/refractory solid tumors

	

• Incidence, nature, and severity of treatment emergent AEs and SAEs, graded according to the NCI CTCAE v5 for the combination of RMC-4630 and cobimetinib

• Incidence and nature of DLTs for the combination of RMC-4630 and cobimetinib

Secondary
 
[Redacted]
	
[Redacted]

Tertiary/Exploratory
 
[Redacted]
	
[Redacted]

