**Table 15 Population Definitions**

Population	Description
Enrolled	All participants who sign an ICF and meet eligibility criteria
Treated	All participants who take at least 1 dose of study intervention
Evaluable	
Evaluable for DLT: All participants in the treated population who have completed the DLT period or who have discontinued due to AEs or death (unless relationship to RMC-4630 and cobimetinib can be ruled out) prior to the end of the DLT period. In addition, participants must receive at least 75% of planned dose (not miss <math>\geq 3</math> doses of RMC-4630 and cobimetinib on D1D2 intermittent schedule and <math>\geq 6</math> doses of cobimetinib on 21 on/7 off schedule, and <math>\geq 8</math> doses of osimertinib within the DLT window for reasons other than toxicity). This population will be the primary population for fitting the dose-toxicity model.
 
Evaluable for efficacy: All participants with measurable disease at baseline, who take at least 1 dose of study intervention and underwent one post-baseline response assessment or who die or had clinical progression prior to first post-baseline response assessment

Safety	All participants who take at least 1 dose of study intervention

Abbreviations: AE, adverse event; DLT, dose-limiting toxicity; ICF, informed consent form.

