**Table 17 Safety Analyses**

Endpoint	Statistical Analysis Methods
Primary	Summaries of AEs, SAEs, and AEs leading to treatment discontinuation and dose modification, changes in laboratory test results and changes in vital signs, and DLT rate
Secondary	Not applicable
Exploratory	Will be described in the statistical analysis plan finalized before database lock

Abbreviations: AE, adverse event; DLT, dose-limiting toxicity; SAE, serious adverse event.

AEs and SAEs will be displayed by combination dose level.

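### On the plain text of section 9.4.2, the primary DLT rate in Table 17 is computed on the Safety Population, so replaced, non-evaluable participants enter its denominator and usually dilute it

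*Combined protocol and SAP*

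**What the plan says.** Section 3.1 makes DLT incidence a primary endpoint: "Incidence and nature of DLTs for the combination of RMC-4630 and cobimetinib". Section 3.2 has the matching endpoint for osimertinib.

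Section 9.4.2 divides the safety analyses between two populations. The first sentence reads "All DLT modeling will be performed on the DLT-evaluable population" and the second "All other safety analyses will be performed on the Safety Population". The section then refers to Table 17 for the safety analyses. The Primary row of Table 17 ends with "changes in laboratory test results and changes in vital signs, and DLT rate" and names no population.

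Table 15 defines the two sets.

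- **Safety:** "All participants who take at least 1 dose of study intervention". There is no condition on exposure or on follow-up through the DLT window.
- **Evaluable for DLT:** the participant completed the DLT period, or stopped early because of an AE or death not shown to be unrelated. In addition, at least 75% of the planned dose was received, and doses missed because of toxicity do not count against the participant. On its use, Table 15 says "This population will be the primary population for fitting the dose-toxicity model".

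Sections 4.1.1.3 (cobimetinib arm) and 4.2.1.3 (osimertinib arm) replace participants who miss too many doses for non-toxicity reasons. Having been treated, these participants stay in the Safety Population.

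Section 9.4 says that the SAP will be finalised before database lock and that the section summarises the planned primary and secondary analyses.

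**The concern.** A DLT rate is meaningful only among people who were exposed enough, and observed long enough, to show a DLT. The protocol builds its evaluable definition and its replacement rule on that idea. A descriptive rate is not modelling, however, so the two-way split in section 9.4.2 sends it to the Safety Population. Someone who missed doses for an unrelated reason, and was replaced for that reason, would then count in the denominator and usually add nothing to the numerator.

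What is at stake is a reported primary result. The study report would show a DLT rate by dose level on one set of participants beside a dose-toxicity model fitted on another. Escalation cohorts have 3 to 6 participants, so one or two people are enough to move the rate visibly.

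The gap matters at least as much in the osimertinib arm. Escalation there follows mTPI-2 rather than the CRM, yet Table 15 still gives an osimertinib dose condition for DLT evaluability. If the dose-toxicity model in Table 15 means the CRM, no analysis in that arm is expressly assigned to the DLT-evaluable set.

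**Working it through.** **The plan's own safety figure.** The only safety precision statement is in section 9.2: with 144 participants, the chance of seeing at least one AE of true incidence 1%, 2% or 5% is 76%, 95% or >99%. The formula 1 − (1 − p)^144 gives 76.5%, 94.5% and 99.9%, which agrees. The total also adds up: 42 + 24 + 78 = 144. These figures concern AEs in general and are not in dispute. The plan states no precision for the DLT rate and no expected non-evaluable share.

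**Inputs.** The MTD cohort has at least 6 participants (section 9.2). The target DLT rate is 30%, with interval 25% to 35% (section 4.1.1.3). The non-evaluable share f of treated participants is assumed to be 5% to 20%.

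**Formula.** Let p_E be the DLT rate among evaluable participants and p_N the rate among non-evaluable participants. Then

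rate on the Safety Population = p_E × (1 − f) + p_N × f.

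This is below p_E whenever p_N is below p_E. If non-evaluable participants have no DLT, it reduces to p_E × (1 − f).

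**Small cohorts, 6 evaluable participants, replaced participants without a DLT:**

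| DLTs | 0 replaced | 1 replaced | 2 replaced |
|---|---|---|---|
| 2 | 2/6 = 33.3% | 2/7 = 28.6% | 2/8 = 25.0% |
| 1 | 1/6 = 16.7% | 1/7 = 14.3% | 1/8 = 12.5% |

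**A true 30% rate among evaluable participants, p_N = 0:**

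- f = 5%: 0.30 × 0.95 = 28.5%
- f = 10%: 0.30 × 0.90 = 27.0%
- f = 15%: 0.30 × 0.85 = 25.5%
- f = 20%: 0.30 × 0.80 = 24.0%

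Setting 0.30 × (1 − f) = 0.25 gives f = 1/6 = 16.7%. Above that share, a dose exactly on target would show a crude rate below 25%.

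**The opposite direction.** Suppose 2 of 6 evaluable participants have a DLT, and one non-evaluable participant also has one. The Safety Population rate is then 3/7 = 42.9%, against 2/6 = 33.3%.

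**The case against.** The best reply is that this is loose drafting rather than a decision. Table 15 names a set for DLT evaluation and calls it the primary population for model fitting, without saying that it serves nothing else. The sponsor may have meant DLT modelling to cover every DLT analysis, and the SAP is still to come. Appendix 10 is blacked out in the public copy, so its handling of DLTs cannot be checked. The study also tests no formal hypotheses, and the rate is descriptive.

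Much of this is fair, and it limits how sure one can be about what will be reported. It does not remove the point. Section 9.4.2 already assigns populations to the primary analyses, and no legible text moves the DLT rate to the evaluable set. An SAP that follows the section literally uses the wrong denominator, and one that departs from it contradicts the protocol.

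Three stronger readings are tempting, and the documents do not support them.

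- A reader might infer that every non-evaluable participant counts as DLT-free, so that the rate is certain to be too low. A participant can have a DLT and also miss doses for unrelated reasons, as the 3/7 example shows. Dilution is the usual direction, not a certainty.
- A reader might infer that anyone who leaves before the end of Cycle 1 is non-evaluable. Table 15 keeps those who stop because of an AE or death unless a relationship to treatment can be ruled out.
- A reader might take the synopsis sentence "DLT events for all participants at a given combination dose level will be entered into the CRM model" as a further, conflicting denominator. It follows directly on the rule that three evaluable participants suffice and a fourth may be enrolled. It most naturally means that the fourth is included, and it sets no denominator.

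**Conclusion.** The point holds for the reported descriptive DLT rate, a primary safety summary. Followed as written, section 9.4.2 places replaced, under-exposed participants in its denominator. With 1 or 2 such participants without a DLT, 33.3% is reported as 28.6% or 25.0%. A 30% rate is reported as 28.5% to 24.0% over an assumed non-evaluable share of 5% to 20%. These sizes rest on that assumed share and on non-evaluable participants having no DLT.

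A reader might go further and infer that the MTD or RP2D would be chosen wrongly. The documents do not show that. In the cobimetinib arm, the MTD comes from the CRM's posterior probability that the DLT rate lies between 25% and 35%, and the CRM is expressly fitted on DLT-evaluable participants. The RP2D is a sponsor decision on all available data, capped at the MTD. The crude Table 17 rate is the stated criterion for neither. It also need not equal a CRM estimate even on the same participants, because the model uses a prior and borrows across doses. The 25% bound above therefore serves only as a yardstick for the size of the shift.

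The change is worth making because the endpoint is primary and the remedy is cheap.

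**What to change.** Replace the first two sentences of section 9.4.2 with text to this effect:

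> All DLT analyses in both arms, meaning the dose-toxicity modelling and the DLT rate in Table 17, use the DLT-evaluable population. Every remaining safety analysis uses the Safety Population. DLT-type events in treated participants who are not DLT-evaluable are listed separately.

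The separate listing ensures that no event is lost when these participants leave the denominator. The SAP should carry the same assignment. The synopsis needs no change.

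The edit alters no sample size, no escalation rule and no clinical rule. Its one downside is that reported DLT rates will usually be slightly higher than on the Safety Population.

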**Table 17 Safety Analyses**

Endpoint	Statistical Analysis Methods
Primary	Summaries of AEs, SAEs, and AEs leading to treatment discontinuation and dose modification, changes in laboratory test results and changes in vital signs, and DLT rate
Secondary	Not applicable
Exploratory	Will be described in the statistical analysis plan finalized before database lock

Abbreviations: AE, adverse event; DLT, dose-limiting toxicity; SAE, serious adverse event.

AEs and SAEs will be displayed by combination dose level.

#### 9.4.3. Other Analyses

Additional efficacy and biomarker exploratory analyses will be described in the statistical analysis plan finalized before database lock.

#### 9.5. Interim Analyses

No formal interim analysis will be conducted. However, as this is an open-label study with regular determinations of dosing levels, several analyses may be conducted at specific points during the study as well as at the end of the study. The Sponsor reserves the right to report interim data after discussion with the principal investigators.

## **APPENDIX 1      REGULATORY, ETHICAL, AND STUDY OVERSIGHT CONSIDERATIONS**

### **REGULATORY AND ETHICAL CONSIDERATIONS**

- This study will be conducted in accordance with the protocol and with the following:
  - Consensus ethical principles derived from international guidelines including the Declaration of Helsinki and Council for International Organizations of Medical Sciences (CIOMS) International Ethical Guidelines
  - Applicable International Council for Harmonisation (ICH) Good Clinical Practice (GCP) guidelines
  - Applicable laws and regulations
- The protocol, protocol amendments, informed consent form (ICF), Investigator's Brochure (IB), and other relevant documents (eg, patient information, advertisements) must be submitted to an Institutional Review Board (IRB) by the investigator and reviewed and approved by the IRB before the study is initiated.
- Any amendments to the protocol will require IRB approval before implementation of changes made to the study design, except for changes necessary to eliminate an immediate hazard to study participants.
- The investigator will be responsible for the following:
  - Providing written summaries of the status of the study to the IRB annually or more frequently in accordance with the requirements, policies, and procedures established by the IRB
  - Notifying the IRB of serious adverse events or other significant safety findings as required by IRB procedures
  - Providing oversight of the conduct of the study at the site and adherence to requirements of 21 CFR, ICH guidelines, the IRB, and all other applicable local regulations

### **FINANCIAL DISCLOSURE**

Investigators and sub-investigators will provide the Sponsor with sufficient, accurate financial information as requested to allow the Sponsor to submit complete and accurate financial certification or disclosure statements to the appropriate regulatory authorities. Investigators are responsible for providing information on financial interests during the course of the study and for 1 year after completion of the study.

## INFORMED CONSENT PROCESS

- The investigator or his/her designated representative will explain the nature of the study to the participant or his/her legally authorized representative and answer all questions regarding the study.
- Participants must be informed that their participation is voluntary. Participants or their legally authorized representative will be required to sign a statement of informed consent that meets the requirements of 21 CFR 50, local regulations, ICH guidelines, Health Insurance Portability and Accountability Act (HIPAA) requirements, where applicable, and the IRB or study center.
- The medical record must include a statement that written informed consent was obtained before the participant was enrolled in the study and the date the written consent was obtained. The authorized person obtaining the informed consent must also sign the ICF.
- Per IRB requirements, participants must be re-consented to the most current version of the ICF(s) during their participation in the study.
- A copy of the ICF(s) must be provided to the participant or the participant's legally authorized representative.

Participants who are re-screened are not required to be re-consented; all re-screening should occur within 5 days of the initial date of the screen failure ([Section 5.4](#))

The investigator or authorized designee will explain to each participant the objectives of the exploratory research. Any remaining mandatory samples may be used for optional exploratory research. Participants will be told that they are free to refuse to participate and may withdraw their consent at any time and for any reason during the storage period.

## DATA PROTECTION

- Participants will be assigned a unique identifier by the Sponsor. Any participant records or datasets that are transferred to the Sponsor will contain the identifier only; participant names or any information which would make the participant identifiable will not be transferred.
- The participant must be informed that his/her personal study-related data will be used by the Sponsor in accordance with local data protection law. The level of disclosure must also be explained to the participant.
- The participant must be informed that his/her medical records may be examined by Clinical Quality Assurance auditors or other authorized personnel appointed by the Sponsor, by appropriate IRB members, and by inspectors from regulatory authorities.

## DISSEMINATION OF CLINICAL STUDY DATA

- The posting of company-Sponsored clinical trial information and tabular study results on the US National Institute of Health (NIH) website ([www.clinicaltrials.gov](http://www.clinicaltrials.gov)) and on other regional clinical trial registries in countries or regions where the clinical trial is conducted, will comply with local regulations.
- Periodic safety reports will be submitted as required by regulation in the countries where the study is conducted.

## DATA QUALITY ASSURANCE

- All participant data relating to the study will be recorded on electronic Case Report Form (eCRF) unless transmitted to the Sponsor or designee electronically (eg, laboratory data). The investigator is responsible for verifying that data entries are accurate and correct by physically or electronically signing the CRF.
- The investigator must maintain accurate documentation (source data) that supports the information entered in the CRF.
- The investigator must permit study-related monitoring, audits, IRB review, and regulatory agency inspections and provide direct access to source data documents.
- Monitoring details describing methods, responsibilities, and requirements, including handling of noncompliance issues and monitoring techniques (central, remote, or on-site monitoring) are provided in the Monitoring Plan.
- The Sponsor or designee is responsible for the data management of this study including quality checking of the data.
- The Sponsor assumes accountability for actions delegated to other individuals (eg, contract research organizations [CROs]).
- Study monitors will perform ongoing source data verification to confirm that data entered into the CRF by authorized site personnel are accurate, complete, and verifiable from source documents; that the safety and rights of participants are being protected; and that the study is being conducted in accordance with the currently approved protocol and any other study agreements, ICH GCP, and all applicable regulatory requirements.
- Records and documents, including signed ICFs, pertaining to the conduct of this study must be retained by the investigator for a period of 2 years following the date a marketing application is approved for the drug for the indication for which it is being investigated; or if no application is to be filed or if the application is not approved for such indication, until 2 years after the investigation is discontinued and US Food and Drug Administration (FDA) is notified (ie, in accordance with 21 CFR 312.62(c), unless local regulations or institutional policies require a longer retention period). No records may be

destroyed during the retention period without the written approval of the Sponsor. No records may be transferred to another location or party without written notification to the Sponsor.

## **SOURCE DOCUMENTS**

- Source documents provide evidence for the existence of the participant and substantiate the integrity of the data collected. Source documents are filed at the investigator's site.
- Data entered on the CRF or entered in the eCRF that are transcribed from source documents must be consistent with the source documents or the discrepancies must be explained. The investigator may need to request previous medical records or transfer records, depending on the study. Also, current medical records must be available.

## **STUDY AND SITE CLOSURE**

The Sponsor reserves the right to close the study site or terminate the study at any time for any reason at the sole discretion of the Sponsor. Study sites will be closed upon study completion. A study site is considered closed when all required documents and study supplies have been collected and a study-site closure visit has been performed.

The investigator may initiate study-site closure at any time, provided there is reasonable cause and sufficient notice is given in advance of the intended termination.

Reasons for the early closure of a study site by the Sponsor or investigator may include but are not limited to:

- Failure of the investigator to comply with the protocol, the requirements of the IRB or local health authorities, the Sponsor's procedures, or GCP guidelines
- Inadequate recruitment of participants by the investigator
- Discontinuation of further study intervention development

## **PUBLICATION POLICY**

- The Sponsor will comply with the requirements for publication of study results, and the results of this study may be published or presented at scientific meetings. In accordance with standard editorial and ethical practice, the Sponsor will generally support publication of multicenter studies only in their entirety and not as individual site data. In this case, a coordinating investigator will be designated by mutual agreement. The coordinating investigator agrees to submit all manuscripts or abstracts to the Sponsor before submission. This allows the Sponsor to protect proprietary information and to provide comments.
- Authorship will be determined by mutual agreement and in line with International Committee of Medical Journal Editors authorship requirements.

